5.2.1.3 Guidance for Diagnosis and Management of Hepatic Events of Clinical Interest

In addition to overdose, hepatic ECIs will include any of the following events. All of these events will require holding study treatment, notification of the Sponsor within 24 hours, and a hepatologist consultation (if necessary). All cases of retreatment and permanent discontinuation must be reported to the Sponsor and recorded in the database. Refer to Section 7.2.3.2 for reporting guidelines and the definition of hepatic ECIs.

a. ALT:

- i. Among subjects with baseline ALT $<2\times$ ULN: ALT $\ge 5\times$ ULN
- ii. Among subjects with baseline ALT $\ge 2 \times ULN$: ALT $> 3 \times$ the baseline level
- iii. ALT >500 U/L regardless of baseline level

Protocol/Amendment No.: 394-06

b. AST:

- i. Among subjects with baseline AST $\leq 2 \times ULN$: AST $\geq 5 \times ULN$
- ii. Among subjects with baseline AST ≥2×ULN: AST >3× the baseline level
- iii. AST >500 U/L regardless of baseline level
- c. Total Bilirubin:
 - i. Among subjects with baseline levels <1.5 mg/dL: a value of >2.0 mg/dL
 - ii. Among subjects with baseline levels that are ≥ 1.5 mg/dL: a value $\ge 2 \times$ the baseline level
 - iii. Total bilirubin >3.0 mg/dL regardless of baseline level
- d. Regardless of laboratory values, hepatic decompensation diagnosed clinically, including:
 - i. New onset clinically detectable ascites
 - ii. Gastrointestinal bleeding suggestive of portal hypertension (e.g., esophageal or gastric varices)
 - iii. Encephalopathy

Immediate assessment

All subjects

- All subjects should be evaluated according to directions below within 72 hours of alert for non-overdose hepatic ECI
- Procedures:
 - Obtain a consultation with a hepatologist (if necessary)
 - Obtain a work-up for hepatitis if there is no underlying hepatitis, including hepatitis A, B,C, D, E, Epstein-Barr virus, and cytomegalovirus
 - Assess for ingestion of drugs/supplements with hepatotoxic potential
 - Assess for alcohol ingestion
 - Assess for potential bacterial infection, biliary obstruction, or occult gastrointestinal bleeding

Product: MK-3475 44

Protocol/Amendment No.: 394-06

• Repeat ALT, AST, T-bil, D-bil, ALP, γ-glutamyl transpeptidase, INR, and complete blood count (CBC) with differential

- o Other laboratories or imaging studies as clinically indicated
- Consider liver biopsy if indicated by hepatologist

Hepatitis C-Infected Subjects (including subjects who previously achieved sustained virologic response for 12 weeks [SVR 12] or sustained virologic response for 24 weeks [SVR24]

• In addition to the above, measure HCV RNA viral load

Hepatitis B-infected Subjects

- In addition to the above, measure HBV DNA, HBsAg, HBeAg, anti-HBc, anti-HBe antibody, and anti-HBs antibody
- Subjects should be questioned about compliance with the use of anti-viral agents.

Permanent Discontinuation Criteria for Subjects with Non-overdose Hepatic ECI

Therapy should also be permanently discontinued for:

- ALT $>20 \times ULN$
- Child-Pugh (CP) score of ≥9 points
- Gastrointestinal bleeding suggestive of portal hypertension (e.g., esophageal or gastric varices)
- New onset clinically detectable ascites
- Hepatic encephalopathy or
- Recurrence of a severe or life-threatening event, or of any of the laboratory abnormalities listed above, that are presumed to be immune-related.

Protocol/Amendment No.: 394-06

Diagnosis and Management of Non-Overdose Hepatic ECIs

HCC subjects are at risk for a range of complications that can cause hepatic laboratory abnormalities with or without clinical decompensation. Those with a history of chronic HCV or HBV infection also have the potential to experience virologic flares. Immune-related hepatitis has been observed in $\sim 1\%$ of subjects who received pembrolizumab. The following section provides further guidance on the diagnosis and management of potential hepatic complications among HCC subjects.

a. Hepatitis B Flare

Hepatitis B flares are characterized by rapid elevations of ALT and AST to >5×ULN and/or >3× baseline. ALT elevation to ≥10×ULN is common. In the absence of hepatic decompensation, ALT/AST elevations are typically isolated (i.e., limited/no elevations of bilirubin/ALP). Subjects who are compliant with anti-viral therapy should have continued suppression of HBV DNA at the time of flare; thus, detection of HBV DNA should prompt questioning of subjects for compliance. Laboratory abnormalities secondary to flare are typically observed for 3-5 weeks.

Among subjects with HBV, a flare should be considered if this pattern is observed and there is no evidence of an alternative etiology. Guidelines for subjects with a diagnosis of HBV flare are as follows:

- Care should be instituted in consultation with a hepatologist (if necessary).
- For subjects who have detectable HBV DNA, re-institute anti-viral therapy.
- If the subject is clinically stable, pembrolizumab dosing may be interrupted for up to 12 weeks. Subjects should undergo weekly laboratory tests including: AST, ALT, ALP, T-bil, D-bil, INR, HBsAg, HBV DNA (if detected at the onset of the flare). Obtain anti-HBe antibody, anti-HBs antibody, and HBV DNA levels (if not detected at the onset of the flare) every 2-3 weeks.
- If ALT returns to normal or Grade 1 (if normal at baseline), or to baseline grade (if Grade 2 at baseline) within 12 weeks, and subjects are clinically stable, subjects may restart pembrolizumab treatment. If these conditions are not met, then pembrolizumab treatment should be permanently discontinued.

b. Hepatitis C Recurrence or Flare

Subjects who achieved SVR 12 or SVR 24 and subjects with ongoing HCV infection are eligible for enrollment. In rare circumstances, HCV subjects who achieve SVR 12 or SVR 24 may relapse at later time points. Relapse is characterized by detection of HCV RNA, often accompanied by ALT elevations

Protocol/Amendment No.: 394-06

to >5×ULN. In the absence of hepatic decompensation, ALT/AST elevations are typically isolated (i.e., limited/no elevations of bilirubin/ALP).

Among subjects with uncontrolled hepatitis C, virologic flares are possible. Hepatitis C flares are characterized by rapid elevations of ALT and AST to >5×ULN and/or >3× baseline along with a rise in HCV RNA. ALT elevation to ≥10×ULN and a 1 log elevation in HCV RNA level are common. In the absence of hepatic decompensation, ALT/AST elevations are typically isolated (i.e., limited/no elevations of bilirubin/ALP). Laboratory abnormalities secondary to flare or recurrence are typically observed for 3-5 weeks.

Guidelines for subjects with recurrent HCV infection or an HCV flare are described below:

i. Recurrent HCV infection:

If the subject entered the study with an HCV RNA test of "Target not Detected" and has confirmed detectable HCV RNA (2 specimens, 1 week apart), then the subject has experienced a late HCV relapse or a recurrent infection.

- Question the subject about use of injection or inhalation drugs
- At the time of first detection of HCV RNA, send a specimen for HCV genotyping
- Measure AST, ALT, ALP, T-bil, D-bil, and INR weekly
- Measure HCV RNA levels every 2 weeks
- Therapy with HCV anti-viral treatments should be strongly considered.

i. HCV Flare:

- At the time of first detection of HCV RNA, send a specimen for HCV genotyping
- Measure AST, ALT, ALP, T-bil, D-bil, INR weekly
- Measure HCV RNA levels every 2 weeks
- Therapy with HCV anti-viral treatments should be strongly considered.
- ii. For both recurrent infection and HCV flare: if ALT returns to normal or Grade 1 (if normal at baseline), or to baseline grade (if Grade 2 at baseline) within 12 weeks, and the subjects are clinically stable, subjects may restart pembrolizumab treatment. If these conditions are not met, then pembrolizumab treatment should be permanently discontinued.

Protocol/Amendment No.: 394-06

c. Immune-related hepatitis

i. Description: Immune-related hepatitis due to pembrolizumab should be suspected if:

- AST or ALT baseline values are less than 2×ULN, and AST or ALT laboratory values increase to ≥5×ULN
- Among subjects with baseline ALT or AST $\ge 2 \times ULN$, levels increase to $> 3 \times ULN$ the baseline level
- AST/ALT >500 U/L regardless of baseline level
- Among subjects with baseline T-bil levels <1.5 mg/dL: a value of >2.0 mg/dL
- Among subjects with baseline T-bil levels that are ≥ 1.5 mg/dL: a value of $\ge 2 \times$ the baseline level, OR
- Total bilirubin >3.0 mg/dL regardless of baseline level.

Immune-related hepatitis is a diagnosis made after excluding other possible etiologies for the change. Viral flare (if applicable), biliary or vascular obstruction, infection, medications, and alcohol use must be ruled out (see below).

ii. Management

- Interrupt pembrolizumab treatment and alert the sponsor as per ECI criteria above for ALT, AST, bilirubin, and hepatic decompensation.
- For Grade 2 AST / ALT elevation or increased bilirubin, administer corticosteroids (initial dose of 0.5-1mg/kg prednisone or equivalent) followed by taper.
- For Grade 3-4 AST / ALT elevation or increased bilirubin, administer corticosteroids (initial dose of 1-2mg/kg prednisone or equivalent) followed by taper.
- Monitor with liver function tests (consider weekly or more frequently until liver enzyme value returned to baseline or is stable).
- If symptoms and laboratory tests resolve to Grade ≤1 or baseline (if abnormal at baseline), taper steroids over 28 days. Study treatment may be restarted after steroid treatment has been tapered to prednisone ≤10 mg/day (or equivalent dose of another agent). Treatment and laboratory results must be reported on a case report form (CRF).

Protocol/Amendment No.: 394-06

• If laboratory abnormalities do not resolve within 3 weeks, or steroids cannot be lowered to ≤10 mg/day (or prednisone equivalent) within 12 weeks, or subjects show evidence of decompensation to Child-Pugh score C (CP C) status or have esophageal or variceal bleeding at any point, treatment must be permanently discontinued. This must be reported on a CRF.

d. Other Hepatic Events of Clinical Interest

- Infection needs to be ruled out with cultures of blood, urine, and ascites (if possible), as well as chest x-ray and abdominal imaging if relevant. If an infection is found, antibiotics should be started.
- If T-bili is elevated above baseline, imaging assessment should be obtained to rule out vascular compromise, biliary obstruction, and/or tumor progression.
 If biliary obstruction is present, consultation with a gastroenterologist and/or an interventional radiologist should be obtained to see if the obstruction may be relieved.
- A careful review of drugs, including herbal and alternative medications, should be obtained, and alcohol use should be ruled out. See Section 5.5.2 for drugs which may interfere with hepatic function.
- For all of these cases, subjects may resume pembrolizumab treatment if they are clinically stable after appropriate therapy or discontinue the causative agent, as long as laboratory values have returned to Grade 1 or baseline (if normal or Grade 1 at start) or to baseline grade within 3 weeks.
- Treatment must be permanently discontinued if the subject is off study treatment therapy for infection, obstruction, or drug/alcohol-related toxicity for more than 3 weeks, or if they have esophageal bleeding, or become CP C at any point.

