12.7 Child-Pugh Score

The Child-Pugh score is used to assess the prognosis of chronic liver disease, mainly cirrhosis. Although it was originally used to predict mortality during surgery, it is now used to determine the prognosis, as well as the required strength of treatment and the necessity of liver transplantation.

Scoring

The score employs five clinical measures of liver disease. Each measure is scored from 1 to 3, with 3 indicating most severe derangement.

Measure	1 point	2 points	3 points
Total bilirubin ¹ (mg/dL)	<2.0	2.0 to 3.0	>3.0
Serum albumin (g/dL)	>3.5	2.8 to 3.5	<2.8
INR ² Or	<1.7	1.7 to 2.3	> 2.3
Prothrombin time, prolongation (seconds)	<4.0	4.0-6.0	>6.0
Ascites	None	Mild (easily controlled by medication)	Moderate to Severe (poorly controlled)
lepatic encephalopathy ³ None		Grade I-II (mild or moderate)	Grade III-IV (severe or coma)

 $^{^{1}}$ In primary sclerosing cholangitis and primary biliary cirrhosis, the bilirubin references are changed to reflect the fact that these diseases feature high conjugated bilirubin levels. The upper limit for 1 point is 68 μ mol/L (4 mg/dL) and the upper limit for 2 points is 170 μ mol/L (10 mg/dL).

In primary sclerosing cholangitis and primary biliary cirrhosis, the bilirubin references are changed to reflect the fact that these diseases feature high conjugated bilirubin levels. The upper limit for 1 point is 68 μ mol/L (4 mg/dL) and the upper limit for 2 points is 170 μ mol/L (10 mg/dL).

² Different textbooks and publications use different measures. Some older reference works substitute PT prolongation for INR

³ Hepatic encephelopathy graded according to West Haven Criteria for Semi-quantitative Grading of Mental Status: Adapted from: Conn H, Lieberthal M. The hepatic coma syndromes and lactulose. Baltimore: Williams & Wilkins; 1979.

Protocol/Amendment No.: 394-06

[figure not shown]
Interpretation

Chronic liver disease is classified into Child-Pugh class A to C, employing the added score from above.

Points	Class	One-year survival	Two-year survival
5–6	A	100%	85%
7–9	В	81%	57%
10–15	С	45%	35%

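### Protocol 5.2.1.3 sets two Child-Pugh thresholds for permanent discontinuation, a score of 9 or more and class C (10–15), and does not say which governs at a score of 9

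*Protocol*

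**What the plan says.** All the stopping text is in Protocol Section 5.2.1.3.

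- **General list.** Its heading is "Permanent Discontinuation Criteria for Subjects with Non-overdose Hepatic ECI", with no limit by cause. It says therapy should also be permanently discontinued for several items, one of which is "Child-Pugh (CP) score of ≥9 points". Gastrointestinal bleeding suggestive of portal hypertension, newly detectable ascites and hepatic encephalopathy are separate items.
- **Part c, immune-related hepatitis.** Treatment must be permanently discontinued if, among other conditions, "subjects show evidence of decompensation to Child-Pugh score C (CP C) status". The restart rule reads: "Study treatment may be restarted after steroid treatment has been tapered to prednisone ≤10 mg/day". It follows resolution of symptoms and laboratory tests and carries no Child-Pugh condition.
- **Part d, other hepatic ECIs.** Treatment must be permanently discontinued after more than 3 weeks off treatment for infection, obstruction or drug/alcohol toxicity, "or if they have esophageal bleeding, or become CP C at any point". The resume rule begins: "For all of these cases, subjects may resume pembrolizumab treatment if they are clinically stable after appropriate therapy". It requires laboratory recovery within 3 weeks and also names no Child-Pugh score.

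Appendix 12.7 sets the classes: A is 5–6 points, B is 7–9 and C is 10–15.

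**The concern.** The general list and the event-specific rules cover the same subjects but draw the Child-Pugh line one point apart, and nothing in the section ranks one above the other. Two investigators facing the same event at a score of 9 could each cite the protocol for a different decision.

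This is a stopping rule for liver decompensation in a trial that requires Child-Pugh A at entry, so the first cost is uneven subject protection. The second is statistical and smaller. Uneven application adds site-to-site variation to exposure and to discontinuation due to AE, which both the Protocol and the SAP list as a safety endpoint. It does not alter the definition of the primary OS analysis, because subjects who stop treatment stay in follow-up and in the ITT population.

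**Working it through.** No sample size, power or alpha figure is involved, and the plan states no figure to reproduce. The check sets the rules against the protocol's own Child-Pugh table.

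**Step 1: scores caught by each rule.**

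| Place in 5.2.1.3 | Child-Pugh criterion | Scores caught | Score of 9 |
|---|---|---|---|
| General list (any non-overdose hepatic ECI) | 9 or more | 9–15 | caught |
| Part c (immune-related hepatitis) | class C | 10–15 | not caught |
| Part d (other hepatic ECIs) | class C | 10–15 | not caught |
| Parts a and b (HBV flare; HCV recurrence or flare) | none stated | – | general list only |

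The sets 9–15 and 10–15 differ by one value, 9, which is class B.

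**Step 2: can a score of 9 arise without another clinical decompensation item?** The score is the sum of five measures, each 1 to 3 points, so it runs from 5 to 15. With no ascites and no encephalopathy (1 point each), bilirubin, albumin and INR/PT must total 9 − 2 = 7. Of the 3 × 3 × 3 = 27 point patterns, those totalling 7 are the three orderings of 1, 3, 3 and the three orderings of 2, 2, 3. That makes 6 patterns.

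One example is bilirubin above 3.0 mg/dL (3), albumin 2.8–3.5 g/dL (2) and INR 1.7–2.3 (2): 3 + 2 + 2 + 1 + 1 = 9. Bilirubin above 3.0 mg/dL is itself a hepatic ECI under 5.2.1.3. The 6 of 27 counts point patterns and is not a probability.

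**Step 3: would sites see such scores?** Yes. The flow chart notes in Section 6.1 require the Child-Pugh score at each visit until the hepatic ECI resolves.

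**Step 4: follow that subject through the text.** The general list gives a permanent stop. Under part c or d the Child-Pugh criterion is not met. If the recovery conditions are then met, the restart or resume sentence applies, and neither sentence excludes someone who had reached 9.

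**Step 5: look for a tie-breaker.** Section 5.8.1 refers to unacceptable adverse events as described in Section 7.2. Section 7.2.3.2 sends hepatic ECI management back to 5.2.1.3. Table 3 covers only non-hepatic immune-related events. None of these settles precedence.

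**The case against.** The best defence is that the rules are cumulative. The general list is not limited by cause, its lead-in contains the word *also*, and parts a–d are introduced as further guidance. Class C lies wholly inside 9 or more, so stopping at 9 satisfies every passage, and the restart wording is only permissive. This reading is available and may be what was meant. But the protocol does not state it, and under it both class C clauses do nothing. The class C clauses also carry the firmer verb: *must*, against *should* in the general list. An investigator who follows the event-specific rule is therefore not plainly wrong.

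The protocol also requires sponsor notification within 24 hours, hepatologist consultation if necessary, and reporting of every retreatment and permanent discontinuation. That makes unnoticed divergence less likely but does not settle the threshold.

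A reader might infer more than the text supports in three ways:

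- **That part d lets subjects resume after new ascites or encephalopathy.** Parts c and d merely omit those items. The general list names them expressly, and the cases part d describes are infection, raised bilirubin or obstruction, and drug or alcohol causes. Silence is not permission.
- **That part d stops treatment only for bleeding or class C.** It also stops for more than 3 weeks off treatment and limits resumption to recovery within 3 weeks.
- **That every hepatic ECI scoring 9 is affected.** The HBV and HCV flare rules contain no class C threshold, so the clash is confined to parts c and d.

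**Conclusion.** Wrong as written: an internal contradiction in a safety stopping rule. The size is narrow. It concerns a subject with a part c or d event who scores exactly 9, meets no other stop item and then satisfies the recovery conditions. The documents give no expected number of such subjects, and no effect on exposure or discontinuation rates can be calculated from them.

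The text does not present two opposed commands. At a score of 9 the general list says treatment *should* stop permanently, and parts c and d leave a permitted route back. The conclusion assumes that the Appendix 12.7 classes apply throughout 5.2.1.3 and that no precedence rule exists elsewhere; none was found in the Protocol or SAP. The omission of ascites and encephalopathy from parts c and d is a secondary gap of the same kind: the protocol does not say whether the general list continues to apply there.

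**What to change.** Reconcile the passages in 5.2.1.3. State one Child-Pugh threshold, as a score or a class consistent with Appendix 12.7, and one list of clinical decompensation events for permanent discontinuation. Have parts c and d refer to that list, or add a sentence saying which passage governs when they differ. If different thresholds by cause are intended, say so and limit the general list accordingly. Which threshold to adopt is for the sponsor's clinical team.

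The cost is a protocol wording change. No analysis, sample size or data collection changes, since the Child-Pugh score is already recorded during hepatic ECIs.

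### The restart rules after a hepatitis B flare or hepatitis C recurrence or flare leave out Grade 1 baseline ALT, so a subject back at a Grade 1 baseline should stop study drug permanently

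*Protocol*

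**What the plan says.** Protocol Section 5.2.1.3 gives separate guidance for four kinds of hepatic event.

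- **Part a, hepatitis B flare.** For a clinically stable subject, restart is allowed on this test: "If ALT returns to normal or Grade 1 (if normal at baseline), or to baseline grade (if Grade 2 at baseline) within 12 weeks". The next sentence is: "If these conditions are not met, then pembrolizumab treatment should be permanently discontinued".
- **Part b, hepatitis C recurrence or flare.** The test is the same, with the same 12-week limit and the same default: "if ALT returns to normal or Grade 1 (if normal at baseline), or to baseline grade (if Grade 2 at baseline".
- **Part c, immune-related hepatitis.** The recovery level is worded differently: "If symptoms and laboratory tests resolve to Grade ≤1 or baseline (if abnormal at baseline". Reaching it starts the steroid taper, and restart follows once prednisone is at or below 10 mg/day.
- **Part d, other hepatic events.** Resumption requires that "laboratory values have returned to Grade 1 or baseline (if normal or Grade 1 at start) or to baseline grade within 3 weeks".

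On eligibility, Table 1 in Section 5.1.2 sets the ALT and AST limit at 5×ULN. The notes to exclusion criteria 25 and 26 (Section 5.1.3) admit controlled hepatitis B and untreated or non-curatively treated hepatitis C.

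**The concern.** In parts a and b, restart at Grade 1 is tied to a normal baseline, and restart at the baseline grade is tied to a Grade 2 baseline. The grade between them has no branch, yet subjects with that baseline can enter the trial. The sentence on unmet conditions then turns the gap into an instruction to stop for good.

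The resulting order makes no evident clinical sense. A subject with a normal baseline may restart at Grade 1, and a subject with a Grade 2 baseline may restart at Grade 2. A subject with a Grade 1 baseline who is back at Grade 1 may not restart. Followed literally, a clinically stable subject at the same ALT grade as on entry loses study drug, in a setting where the protocol stresses the lack of alternatives. Sites that guess at the intent may also guess differently.

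**Working it through.** The plan gives no figure to reproduce. The check crosses baseline ALT grade with recovered ALT grade (within 12 weeks, clinically stable) and reads each cell strictly, without inferring that a lower ALT satisfies a higher permitted level.

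**Is a Grade 1 baseline possible?** Yes. Entry is allowed up to 5×ULN, parts a and b themselves presuppose Grade 2 baselines, and part d names a Grade 1 start. Grade 1 lies between normal and Grade 2, so the CTCAE cut-offs, which the protocol does not reproduce, are not needed.

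**Two readings of the first parenthesis.** On reading A, the normal-baseline condition governs both recovery levels before it (normal and Grade 1). On reading B, it governs only Grade 1. Entries show whether restart is allowed.

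| Baseline | Reading | Recovered to normal | Recovered to Grade 1 | Recovered to Grade 2 |
|---|---|---|---|---|
| Normal | A | yes | yes | no |
| Normal | B | yes | yes | no |
| Grade 1 | A | no | **no** | no |
| Grade 1 | B | yes | **no** | no |
| Grade 2 | A | no | no | yes |
| Grade 2 | B | yes | no | yes |

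On reading A, parts a and b give the Grade 1-baseline subject no branch at all. On reading B, ALT must become fully normal. The cell for Grade 1 returning to Grade 1 is a no on both.

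**Return to own baseline grade.**

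- Parts a and b: normal yes, Grade 1 no, Grade 2 yes, so 2 of 3 on either reading.
- Part c accepts Grade 1 or lower, or an abnormal baseline: 3 of 3 count as recovered.
- Part d accepts Grade 1 or baseline for a normal or Grade 1 start, otherwise the baseline grade: 3 of 3.

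**With Grade 1 added to the first parenthesis**, the Grade 1 row becomes yes / yes / no on both readings. Two cells change on reading A and one on reading B. No cell in the other rows changes, and return to own baseline becomes 3 of 3.

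**The case against.** The strongest reply is that the text is being read too literally. On reading A, the same strictness would bar a Grade 2-baseline subject who recovers to normal, which no investigator would apply. If an investigator may infer better-than-baseline there, return to baseline may be inferred for Grade 1, and parts c and d show that this was probably meant.

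The rule is also guidance. It is introduced with "Guidelines for subjects with a diagnosis of HBV flare are as follows" and says should, whereas parts c and d use must: "have esophageal or variceal bleeding at any point, treatment must be permanently discontinued", and "Treatment must be permanently discontinued if the subject is off study treatment therapy for infection, obstruction, or drug/alcohol-related toxicity for more than 3 weeks". Section 5.8.1 leaves general room to begin treatment again when medically appropriate, unless the subject has been unblinded. Section 5.2.1.3 requires retreatment to be reported to the Sponsor. Finally, the comparison with parts c and d is uneven: they work to 3 weeks for laboratory recovery, not 12, and part c adds the steroid condition.

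Most of this limits the point without removing it. The likely intent is clear, but the written default says the opposite. Should is weak comfort, because the section's general list of permanent-stop criteria, including ALT above 20×ULN and encephalopathy, uses the same word. The discretion in Section 5.8.1 and the reporting duty set no ALT level for a Grade 1 baseline and do not override a specific instruction. Parts c and d govern other causes, so they neither contradict parts a and b nor fill the gap. They are used here only to show how the drafters treated a Grade 1 start elsewhere. The 2-of-3 figure counts cases in the rule and says nothing about how often they arise.

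**Conclusion.** The point holds. Parts a and b are wrong as written, through a minor drafting omission: on either reading, a Grade 1-baseline subject back at Grade 1 should stop permanently, while a Grade 2-baseline subject may restart at a higher ALT. Nothing is claimed about a Grade 2 baseline that falls to Grade 1, which the text also does not spell out.

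The consequence is limited. The error adds no toxicity, and under Section 5.8.1 a subject who stops treatment stays in follow-up. No effect on type I error, power or the ITT analysis of OS is claimed.

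The number affected cannot be derived and is probably small. A subject must have a Grade 1 baseline and a flare or recurrence, return to Grade 1 within 12 weeks, be clinically stable, and meet none of the permanent-stop criteria in Section 5.2.1.3. Treatment is capped at 35 doses, with up to 17 more in a second course, so few subjects, if any, may still be on drug under Amendment 06. The documents do not state how many.

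**What to change.** In Section 5.2.1.3, parts a and b, extend the first parenthesis so that it covers a normal *or Grade 1* baseline. This follows the part d pattern and leaves the normal and Grade 2 rules as they are.

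If the sponsor also wants to settle the Grade 2 baseline that improves to Grade 1, the test could be recovery to Grade 1 or lower, or to the baseline grade. On the table above, that gives yes / yes / no for normal and Grade 1 baselines and yes / yes / yes for Grade 2.

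The cost is two added words in two places. Because a dosing rule changes, the edit needs a protocol amendment with regulatory and IRB/IEC review (Section 12.1). It can go into the next amendment and does not justify one of its own.
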